4. ANALYSIS SETS

Data for all patients will be assessed to determine if patients meet the criteria for inclusion in each analysis population prior to releasing the database and classifications will be documented per Pfizer’s standard operating procedures.

Only patients who signed informed consent will be included in the analysis sets below.

Table 4 summarizes the use of the analysis sets for efficacy, safety, baseline characteristics, and exposure.

Table 4. Statistical Analyses by Analysis Set

Endpoints	Full Analysis Set	Per Protocol Analysis Set	Safety Analysis Set
Baseline Characteristics	✓		✓
Prior and Concomitant Therapies	✓		✓
Exposure			✓
Efficacy: Primary	✓	✓	
Efficacy: Secondary	✓		
CCI	■		
Safety			✓

4.1. Full Analysis Set

The full analysis set (FAS) will include all randomized patients. Patients will be classified according to the study treatment assigned at randomization.

4.2. Safety Analysis Set

The safety analysis set will include all patients who receive at least one dose of study drug. Patients will be classified according to the study treatment assigned at randomization unless the incorrect treatment(s) was/were received throughout the dosing period in which case patients will be classified according to the first study treatment received.

4.3. Other Analysis Sets

4.3.1. Per-protocol analysis sets

Per protocol (PP) analysis set is a subset of the FAS and will include patients who do not meet any of the following criteria that could impact the primary objectives of the study. Patients who meet any of the following criteria will be excluded from the PP analysis set for PFS by BICR.

- Patient did not receive at least one dose of the randomized study treatment
- Patient without a tumor assessment >7 weeks after randomization (unless PD by BICR or death is observed before that time in which case the patient will not be excluded from the PP analysis set)
- Patient without measurable disease at baseline by BICR
- ECOG status > 1
- Patient does not meet Inclusion Criteria 1, 2 or 3
 1. Histologically confirmed epithelial ovarian, fallopian tube, or peritoneal cancer, including malignant mixed Müllerian tumors with high grade serous component.
 2. Platinum-resistant/refractory disease, defined as disease progression within 180 days following the last administered dose of platinum therapy (resistant), or lack of response or disease progression while receiving the most recent platinum-based therapy (refractory), respectively.
 3. Received up to 3 lines of systemic anticancer therapy for platinum-sensitive disease, most recently platinum-containing, and no prior systemic therapy for platinum-resistant disease.

Note that the protocol only requires that patients have measurable disease at baseline as per investigator assessment. However, since PFS by BICR is the primary endpoint, “patient without measurable disease at baseline by BICR” will be used as a criterion to exclude patients from the PP analysis set for this sensitivity analysis of the PFS by BICR primary endpoint.

Patients who meet any of the following criteria will be excluded from the PP analysis set for OS.

- Patient did not receive at least one dose of the randomized study treatment
- ECOG status > 1
- Patient does not meet Inclusion Criteria 1, 2 or 3

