30. **Premedications:** For additional information about premedications for PLD and avelumab, see [Section 5.2.3.1](#) and [Section 5.2.3.3](#).

31. **Tumor Assessments:** Tumor assessments will include all known or suspected disease sites. Tumor assessments must include chest, abdomen and pelvis CT or MRI scans and will be conducted every 8 weeks until documented disease progression as assessed by BICR regardless of subsequent anti-cancer therapy. Brain scans will be performed at baseline only if disease is suspected and on study as appropriate to follow disease. Baseline central nervous system (CNS) imaging is not required with the exception of symptomatic patients to rule out CNS metastases. A bone scan (bone scintigraphy) or ¹⁸F-FDG-PET/CT is required at baseline only if disease is suspected and then every 16 weeks only if bone metastases are present at baseline. Otherwise, bone imaging is required only if new bone metastases are suspected. Bone imaging is also required at the time of CR confirmation for patients who have bone metastases. MRI is acceptable for bone imaging if consistent with local practice. CT or MRI scans to be done every 2 cycles (every 8 weeks) (window of 5 days prior to dosing is allowed) throughout the study. In case partial response (PR), complete response (CR) or Progressive Disease (PD) is observed according to RECIST v.1.1 (Appendix 3) and CCI (Appendix 4) (Nishino 2014),⁴⁹ confirmation CT or MRI should be performed no sooner than 4 weeks after the first documentation of response. Tumor assessment should be repeated at the End of Study visit if more than 4 weeks have passed since the last evaluation. All radiographic images will be collected and will be objectively verified by a BICR independent third-party core imaging laboratory as described in Study Manual. See Section 7.6 for additional information.
32. **Patient-Reported Outcome Questionnaire:** EORTC QLQ-C30, EORTC QLQ-OV28, and EQ-5D-5L are to be administered on Day 1 of Cycle 1, Day 1 of each subsequent cycle, End of Treatment/Withdrawal Visit and the 30, 60 and 90 day Safety Follow-up visits prior to any study or medical procedure. See Appendix 6.
33. **Adverse Event (AE) Assessments:** Adverse events should be documented and recorded in the CRF. The National Cancer Institute Common Terminology Criteria for Adverse Events (NCI CTCAE) version (v) 4.03 will be used. (Appendix 5). See Section 8.2 for Reporting Period details.

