6.1.2. Progression-free survival as assessed by BICR per RECIST v1.1

6.1.2.1. Primary analysis

The following analyses will be based on the FAS using the strata assigned at randomization. Progression of disease (PD) below refers to PD by BICR assessment.

Progression-Free Survival (PFS) is defined as the time from date of randomization to the date of the first documentation of PD or death due to any cause, whichever occurs first.

PFS data will be censored on the date of the last adequate tumor assessment for patients who do not have an event (PD or death), for patients who start a new anti-cancer therapy prior to an event (see Section 5.2.6) or for patients with an event after 2 or more missing tumor assessments. Patients who do not have an adequate baseline tumor assessment or who do not have an adequate post-baseline tumor assessment will be censored on the date of randomization unless death occurred on or before the time of the second planned tumor assessment (ie, \leq 16 weeks after the date of randomization) in which case the death will be considered an event.

090177e19142bcd4\Approved\Approved On: 09-Jul-2019 05:44 (GMT)

In this study antitumor activity will be assessed through radiological tumor assessments conducted at screening and every 8 weeks until disease progression regardless of initiation of subsequent anti-cancer therapy. The allowable time window for disease assessments is 5 days prior to dosing while on treatment and whenever disease progression is suspected (eg, symptomatic deterioration).

The censoring and event date options to be considered for the PFS and DR analysis are presented in Table 9.

$$\text{PFS (months)} = [\text{date of event or censoring} - \text{date of randomization} + 1] / 30.4375$$

Table 9. Outcome and event dates for PFS and DR analyses

Scenario	Date of event/censoring	Outcome
No adequate baseline assessment	Date of randomization ^a	Censored ^a
PD or death - After at most one missing or inadequate post-baseline tumor assessment, OR - ≤ 16 weeks after the date of randomization	Date of PD or death	Event
PD or death - after 2 or more missing or inadequate post-baseline tumor assessments	Date of last adequate tumor assessment ^b documenting no PD before new anti-cancer therapy is given or missed tumor assessments	Censored
No PD and no death	Date of last adequate tumor assessment ^b documenting no PD before new anti-cancer therapy is given or missed tumor assessments	Censored

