Treatment discontinuation due to 'Disease progression' without documented progression	Not applicable	Information is ignored. Outcome is derived based on documented progression only.
New anti-cancer therapy given	Date of last adequate tumor assessment ^b documenting no PD before new anti-cancer therapy is given or missed tumor assessments	Censored

^a However if the patient dies ≤16 weeks after the date of randomization the death is an event with date on death date

^b If there are no adequate post-baseline assessments prior to PD or death, then the time without adequate assessment should be measured from the date of randomization; if the criteria were met the censoring will be on the date of randomization.

The primary efficacy analysis will compare the PFS time based on BICR assessment between each of the experimental arms and the control arm, and will be performed using a 1-sided stratified log-rank test as described in Section 5.1.

The treatment effect will be estimated using a Cox's Proportional Hazard model stratified by the randomization strata to calculate the hazard ratio. Each stratum will define a separate

090177e19142bcd4\Approved\Approved On: 09-Jul-2019 05:44 (GMT)

baseline hazard function (using the 'STRATA' statement in SAS PROC PHREG), ie for the *i*-th stratum the hazard function is expressed as: $h(i;t) = h(i,0;t) \exp(x\beta)$, where $h(i,0;t)$ defines the baseline hazard function for the *i*-th stratum and *x* defines the treatment arm (0=control arm, 1= experimental arm) and β is the unknown regression parameter.

Ties will be handled by replacing the proportional hazards model by the discrete logistic model (Ties=Discrete option in SAS PROC PHREG).

In order to account for the group sequential design in this study, the repeated CI (RCI) method (Jennison and Turnbull, 2000), will be used to construct the 2-sided RCIs for the hazard ratio at the interim and the final analyses of PFS.

In addition, the unadjusted 95% CIs for the hazard ratio will also be reported at the interim and the final analyses for PFS.

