6.2.2.2. Sensitivity analyses for progression-free survival

The following sensitivity analyses will be performed to explore the robustness of the primary analysis results. These analyses are regarded as purely exploratory. The sensitivity analyses will repeat the primary analysis (p-value, HR and 95% CIs) described in Section 6.1.2.1 with the modifications below:

- PFS based on BICR assessment and counting all PD and deaths as events regardless of missing assessments or timing of the event
- PFS based on BICR assessment on the PP analysis set for PFS
- PFS based on BICR assessment using an unstratified analysis
- PFS based on BICR assessment using strata derived according to eCRF data instead of those entered in IRT. See Section 6.2.2.1 for the derivation associated with the stratification factor of bulky disease.
- PFS based on BICR assessment modifying the censoring rules in Table 9 to consider all deaths as events
- PFS based on BICR assessment modifying the censoring rules in Table 9 with initiation of subsequent anti-cancer therapies not used as a censoring reason

Methods for evaluating the validity of model assumptions

The same methodology described in Section 6.2.2.1 for OS will be used for PFS based on BICR assessment.

BICR vs Investigator assessment

A summary of the BICR assessment versus investigator assessment will be provided including numbers of concordant and discordant assessments as well as the number of cases where PFS event was assessed at different timepoints based on BICR and investigator assessments.

Table 11 outlines the possible outcomes by investigator and BICR (Amit et al. 2011).

Table 11. Possible Outcomes for Investigator vs BICR

		BICR	
		Event	No Event
Investigator	Event	$a = a_1 + a_2 + a_3$	b
	No Event	c	d

a1: number of agreements on timing and occurrence of event;
 a2: number of times agreement on event but INV declares event later than BICR;
 a3: number of times agreement on event but INV declares event earlier than BICR;
 $N = a + b + c + d$.

The timing agreement of event is defined as a window of ± 7 days.

The following measure of discordance will be calculated for each treatment arm:

- Total Event Discrepancy Rate: $(b+c) / N$
- Early Discrepancy Rate (EDR): $(a_3+b) / (a+b)$
- Late Discrepancy Rate (LDR): $(a_2+c) / (a_2+a_3+b+c)$
- Overall Discrepancy Rate: $(a_2+a_3+b+c) / N$

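### The per-protocol set for PFS keeps deaths before week 7 but drops treated, eligible patients who die in weeks 7 to 16 with no scan after week 7, although the primary rule can count those deaths as events (minor).

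*SAP*

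**What the plan says.** **PP set.** SAP 4.3.1 lists the grounds for removal from the PP set for PFS by BICR. One is "Patient without a tumor assessment >7 weeks after randomization (unless PD by BICR or death is observed before that time"), in which case she stays in. The other grounds are not receiving the randomized treatment, no measurable disease by BICR at baseline, ECOG status above 1, and failing inclusion criterion 1, 2 or 3.

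**Primary PFS rule.** SAP 6.1.2.1 censors a patient with no adequate baseline or post-baseline assessment at randomization, "unless death occurred on or before the time of the second planned tumor assessment", which it sets at 16 weeks. Table 9 makes any PD or death within 16 weeks an event. Its footnote a repeats this for a patient with no adequate baseline: "the death is an event with date on death date". Deaths that follow new anti-cancer therapy are censored.

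**Scan timing.** SAP 6.1.2.1 describes "radiological tumor assessments conducted at screening and every 8 weeks until disease progression". It adds: "The allowable time window for disease assessments is 5 days prior to dosing while on treatment".

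**Role of the PP analysis.** SAP 6.2.2.2 lists "PFS based on BICR assessment on the PP analysis set for PFS" among six PFS sensitivity analyses and says of them: "These analyses are regarded as purely exploratory". Protocol 9.3.1.2 calls the PP analysis supportive and describes the set in terms of measurable disease by BICR and the absence of key deviations that could affect PFS.

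**The concern.** The exception in SAP 4.3.1 is evidently there so that a patient is not dropped merely for having an event before she could be scanned. Its limit of 7 weeks falls before the first scan is due, and well before the 16 weeks that the primary analysis uses for the same situation. Between the two limits, a death with no scan after week 7 is an event in the primary analysis and an exclusion in the PP analysis.

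A patient who dies after week 7 but before her first scan has missed no assessment and broken no eligibility rule. She is removed because of when she died. A PP set should be selected on eligibility and conduct. Selecting on the outcome being analysed can tilt the comparison: if more such deaths occur in one arm, removing them favours that arm.

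**Working it through.** **Stated figure.** No figure in the plan is in dispute. The nearest is the 93% power for PFS with 325 events, HR 0.6 and one-sided alpha 0.001. It reproduces: √(325/4) × −ln 0.6 = 9.014 × 0.5108 = 4.604; 4.604 − 3.090 = 1.514; Φ(1.514) = 93.5%. With the two-look O'Brien-Fleming-type spending at 267 and 325 events, power is 93.3% and the interim boundary is z = 3.4474 in absolute value, as in SAP Table 5. The primary design is not in question.

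**Rules side by side.** Take a treated, eligible patient with adequate baseline imaging, no scan after week 7, no PD by BICR and no new anti-cancer therapy.

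| Death at | Primary analysis (Table 9) | PP set (4.3.1) |
|---|---|---|
| week 6 | event | kept |
| week 7.5 | event | removed |
| week 12 | event | removed |
| week 17 | censored (week 8 and 16 scans both missed) | removed |

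The mismatch runs from week 7 to week 16. It concerns deaths only: PD by BICR after week 7 needs a scan after week 7, which satisfies the criterion.

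**Part of the gap is structural.** Week 8 is day 56. Less the 5-day window, the earliest on-schedule scan is at 51/7 = 7.3 weeks. A death between week 7 and the first scan involves no missed assessment.

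**Size.** Inputs:
- Patients per arm: 550/3 = 183.3 (SAP 5.1.1).
- Median OS: 12 months for control and 20 months for experimental, exponential (SAP 5.1.1).
- Weeks per month: 30.4375/7 = 4.348 (SAP 5.2.8).
- Share of deaths in weeks 8 to 16 with no scan after week 7: not given in the documents; range 0 to 30% assumed.

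Formula: S(t) = 0.5^(t/median), with t in months.

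| | Control, 12 months | Experimental, 20 months |
|---|---|---|
| S(7 wk) | 0.9112 | 0.9457 |
| S(8 wk) | 0.8992 | 0.9382 |
| S(16 wk) | 0.8085 | 0.8803 |
| Deaths, weeks 7–8 | 0.0120 × 183.3 = 2.2 | 0.0075 × 183.3 = 1.4 |
| Deaths, weeks 8–16 | 0.0907 × 183.3 = 16.6 | 0.0580 × 183.3 = 10.6 |
| Removed if 0% unscanned | 2.2 | 1.4 |
| Removed if 30% unscanned | 2.2 + 0.3 × 16.6 = 7.2 | 1.4 + 0.3 × 10.6 = 4.6 |

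These counts lean high. They do not subtract deaths after new anti-cancer therapy (censored in the primary analysis), deaths after PD by BICR before week 7 (already events, and kept in the PP set), or patients never dosed (removed on another ground).

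**Effect on the hazard ratio.** In a simulation with 183 patients per arm, exponential PFS medians of 3.5 and 5.8 months and censoring at 24 months, events in weeks 7 to 16 were removed at random and the Cox model refitted. Removing 2.2 control and 1.4 experimental events multiplies the HR by about 0.999. Removing 7.2 and 4.6 multiplies it by about 0.998. Removal at random within the window, in these proportions, is an assumption.

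**The case against.** **It is exploratory.** This is one of six PFS sensitivity analyses. Alpha, power, stopping and the primary test do not use it. Two of the others, run on the full analysis set, address the handling of deaths directly: one counts every PD and death whatever the missed scans or timing, the other counts all deaths. This stands, and it is why the point is minor.

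**The numbers are small.** A reader might take every death in weeks 7 to 16, about 19 in the control arm (2.2 + 16.6) and 12 in an experimental arm (1.4 + 10.6), as primary events lost. The documents do not support that. It would require that nobody who dies in that window is scanned after week 7, although scans are due at week 8, whenever progression is suspected and, in the original schedule, at end of treatment. Not all of those deaths are primary events either. Entry also requires ECOG 0 to 1 and a life expectancy of at least 3 months, so a constant hazard from randomization probably overstates early deaths. Even removing all 19 and 12 multiplies the simulated HR by only about 0.995.

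**A missed week-8 scan is a lapse.** A patient who dies unscanned in weeks 9 to 16 has missed a scheduled assessment, and a PP set may reasonably require one. This partly stands, but not for deaths before the first scan.

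**A 16-week limit only moves the cut-off.** True, but an unscanned death after week 16 is censored in the primary analysis, so removing that patient loses no primary event.

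**The wording could mean the time of the missing scan.** That reading would keep deaths before the first scan, but the only time the criterion states is 7 weeks, and a programmer would code 7 weeks.

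**Conclusion.** The inconsistency is real and minor. As written, the PP set for PFS removes some patients because they died between weeks 7 and 16 unscanned, while the primary rule counts those deaths unless new anti-cancer therapy came first. About 2 control and 1 experimental patient per arm of 183 are affected by deaths in weeks 7 to 8 alone. The range is about 2 to 7 and 1 to 5 if 0 to 30% of deaths in weeks 8 to 16 also lack a scan. This rests on the plan's exponential OS medians and on that assumed share.

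A reader might infer that the PP result could falsely confirm or contradict the primary PFS finding. The documents do not support going that far. The analysis is exploratory, and the HR barely moves when deaths are lost in the proportions the planned medians imply. A material distortion would need these deaths to be clearly unbalanced between arms, and nothing in the documents shows that. The primary test in the full analysis set, its alpha and its power are not affected.

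**What to change.** In SAP 4.3.1, change the exception to: *unless PD by BICR is observed, or death occurs on or before 16 weeks after randomization, in which case the patient will not be excluded*. This matches Table 9. Report by arm the number of patients excluded under this criterion.

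The cost is one phrase, one programming condition and one line in a disposition table. Protocol section 9 says the final analysis has been completed, so for results already produced the by-arm count and one rerun of the PP analysis would settle the matter. The small downside is that patients who die in weeks 9 to 16 after missing the week-8 scan stay in the PP set.

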4.3.2. PK analysis sets

The PK concentration analysis set is a subset of the safety analysis set and will include patients who have at least one post-dose concentration measurement above the lower limit of quantitation (LLQ) for avelumab or doxorubicin.

The PK parameter analysis set is a subset of the safety analysis set and will include patients who have at least one of the PK parameters of interest for avelumab or doxorubicin.

4.3.3. Biomarker analysis sets

The biomarker analysis set for biomarkers that are measured only at screening is a subset of the safety analysis set and will include patients who have at least one screening biomarker assessment.

The biomarker analysis set for biomarkers that are measured sequentially is a subset of the safety analysis set and will include patients who have at least one baseline and one on-treatment biomarker assessment for the same marker.

Analysis sets will be defined separately for blood-based and tumor tissue-based biomarkers.

4.3.4. Immunogenicity analysis set

The immunogenicity analysis set is a subset of the safety analysis set and will include patients who have at least one ADA/nAb sample collected for avelumab in the avelumab containing arms.

5. GENERAL METHODOLOGY AND CONVENTIONS

5.1. Hypotheses and Decision Rules

5.1.1. Hypotheses and sample size determination

The study is designed to test, in parallel, the following hypotheses:

$$H_{01}: HR_{OS(avelumab/PLD)} \geq 1, \text{ versus } H_{a1}: HR_{OS(avelumab/PLD)} < 1$$

$$H_{02}: HR_{OS(avelumab+PLD/PLD)} \geq 1, \text{ versus } H_{a2}: HR_{OS(avelumab+PLD/PLD)} < 1$$

$$H_{03}: HR_{PFS(avelumab/PLD)} \geq 1, \text{ versus } H_{a3}: HR_{PFS(avelumab/PLD)} < 1$$

$$H_{04}: HR_{PFS(avelumab+PLD/PLD)} \geq 1, \text{ versus } H_{a4}: HR_{PFS(avelumab+PLD/PLD)} < 1$$

where HR_{OS} represents the hazard ratio for OS in each of the experimental arms vs the control arm, and HR_{PFS} represents the hazard ratio for PFS by BICR assessment in each of the experimental arms vs the control arm.

The treatment effects on the primary PRO endpoint, time to deterioration (TTD), will also be tested.

$$H_{05}: HR_{TTD(avelumab/PLD)} \geq 1, \text{ versus } H_{a5}: HR_{TTD(avelumab/PLD)} < 1$$

[figure not shown]
$$H_{06}: HR_{TTD(avelumab+PLD/PLD)} \geq 1, \text{ versus } H_{a6}: HR_{TTD(avelumab+PLD/PLD)} < 1$$

where HR_{TTD} represents the hazard ratio for TTD in each of the experimental arms vs the control arm.

Approximately 550 patients will be randomized to the treatment arms using a 1:1:1 randomization, stratified by platinum-refractory or platinum-resistant status, number of prior regimens (1 vs 2 or 3), and bulky disease (defined as presence of a tumor ≥ 5 cm) vs not.

Overall type I-error will be maintained at or below 1-sided 0.025 by allocating 0.0115 alpha to each of the two OS comparisons and 0.001 to each of the two PFS comparisons. A gatekeeping procedure will be used to allow further testing of TTD for patients as described in Figure 1. The significance levels for each test will also take into account the group sequential nature of the design.

Figure 1 Testing Strategy

For each of the two OS comparisons, 196 OS events will be required to have at least 90% power to detect a hazard ratio of 0.6 using a 1-sided log-rank test at a significance level of 0.0115, and a 2-look group-sequential design with Lan-DeMets (O'Brien-Fleming) α -spending function to determine the efficacy boundary and a Gamma Family (-10) β -spending function to determine the non-binding futility boundary.

For each of the two PFS comparisons, 325 PFS events by BICR assessment will provide 93% power to detect a HR of 0.6 using a 1-sided log rank test at a significance level of 0.001, and a 2-look group sequential design with Lan-DeMets (O'Brien-Fleming) α -spending function to determine the efficacy boundary and a Gamma Family (-10) β -spending function to determine the non-binding futility boundary.

The analysis cut-off date for the test of the 4 primary hypotheses for OS and PFS will be the same for the IA and, if applicable, for the final analysis. The hypotheses of TTD will be tested at the time of the primary OS and PFS analyses.

The sample size for this study is determined based on the assumptions that the median OS and PFS in control arm is 12 months and 3.5 months, respectively (Gordon et al, 2001; Colombo et al, 2012), and that treatment with avelumab alone or avelumab in combination with PLD is expected to increase the median OS and median PFS to ≥ 20 months and ≥ 5.8 months, respectively, corresponding to a hazard ratio (HR) of ≤ 0.6 under the exponential model assumption. The sample size further assumes a 5% drop-out rate for OS and 15% drop-out rate for PFS within each treatment arm and a non-uniform patient accrual over a 19-month period. The data cut-off for the primary OS and PFS analyses will occur after the target number of events for both endpoints has been reached within each comparison and the last patient randomized in the study has been followed for at least 12 months after randomization.

